This study will adhere to the principles outlined in the UK Policy Frame Work for Health and Social Care Research It will be conducted in compliance with the protocol, the Data Protection Act and other regulatory requirements as appropriate.

Table of Contents

1. INTRODUCTION	7
1.1 BACKGROUND	7
2. STUDY OBJECTIVES	9
3. STUDY DESIGN	9
4. PARTICIPANT ENTRY	11
5. ADVERSE EVENTS	13
5.1 DEFINITIONS	13
5.3 REPORTING PROCEDURES	13
6. STUDY TEM AND VISIT ORGANISATION	14
7. STATISTICS AND DATA ANALYSIS	17
8. REGULATORY ISSUES	19
8.1 ETHICS APPROVAL	19
8.2 CONSENT	19
8.3 CONFIDENTIALITY	19
8.4 INDEMNITY	19
8.5 SPONSOR	19
8.6 FUNDING	20
8.7 AUDITS	20
9. STUDY MANAGEMENT	20
10. DATA MANAGEMENT	20
PUBLICATION POLICY	22
10. REFERENCES	23
APPENDICES	24

GLOSSARY OF ABBREVIATIONS

ASHA	Accredited Social Health Activist
CC	Community Clinics
CEBs	Census enumeration blocks
CHT	Chittagong Hill Tracts
COPD	Chronic Obstructive Pulmonary Disease
CVD	Cardiovascular Disease
ECG	Electrocardiogram
EDTA	Ethylenediaminetetraacetic acid
GN	Grama Niladhari
ICT	Islamabad Capital Territory
NCD	Non-Communicable Disease
NIHR	National Institute for Health Research
LVH	Left Ventricular Hypertrophy
UD	Urban Dispensary
PMCU	Primary Medical Care Units
QC	Quality Control
SDMC	South Delhi Municipal Corporation
T2D	Type-2 Diabetes
WHO	World Health Organization

KEYWORDS

Cardiovascular Disease; Type-2 Diabetes; Surveillance

STUDY SUMMARY

TITLE Understanding the patterns and determinants of health in South Asian people - South Asia Biobank

DESIGN Cross-sectional study

AIMS We aim to establish a network of community based, NCD surveillance sites in Bangladesh, India North, India South, Pakistan and Sri Lanka

OUTCOME MEASURES Hypertension; diabetes; chronic kidney disease, CVD; stroke

POPULATION South Asian Population

ELIGIBILITY Inclusion criteria will be:

- Age 18+ years
- Male or Female
- South Asian ancestry
- Permanent resident of the surveillance site (resident for >12 months)

Exclusion criteria will be:

- Planning to leave the study site within the next 12 months
- Cancer or other serious illness expected to reduce life expectancy to less than 12 months
- Unable or unwilling to give consent

DURATION 20 years

REFERENCE DIAGRAM

[if appropriate]

1. INTRODUCTION

1.1 BACKGROUND

Importance of cardiovascular disease and type-2 diabetes in South Asians

Cardiovascular disease (CVD) and type-2 diabetes (T2D) are leading, closely interlinked global health challenges: 422M people live with T2D, while CVD caused 17.5M deaths in 2012 (31% of global mortality).^{1,2} The burden of T2D and CVD are especially high in South Asia, the most populous and densely populated region of the world (1.73 billion people in 2015, 25% of world population). India alone is home to ~74M people with T2D.³ Furthermore, the incidence of CVD is rising sharply across South Asian populations, in direct contrast to the falling CVD mortality rates observed in the US and most Western European countries.⁴ T2D and CVD pose enormous economic burdens on individuals, families and healthcare systems, and thus make a major contribution to poverty, inequality and social instability across the South Asia region.⁵ The World Health Organisation, United Nations and the International Diabetes Federation recognise that there is an urgent need for action to reverse the current epidemics of CVD and T2D in South Asians.

Importance of understanding risk relationships for NCD prevention

Accurate knowledge of the relationships between clinical and laboratory measures of metabolic and cardiovascular risk, with future incidence of T2D and CVD is an essential component of population based strategies for prevention of NCDs.⁶ Appreciation of risk relationships raises awareness of disease determinants, guides appropriate pharmacological and lifestyle intervention, and informs public health policy and rational resource allocation. Identification of the primary risk factors for CVD and T2D in the population, and the implementation of systematic approaches to NCD risk stratification and prevention (including through use of multivariate risk prediction tools), have contributed to the ~70% reduction in incidence of CVD documented in Western Europe and USA over the last two decades.⁷ However national mortality statistics from the UK show that health gains in UK South Asians have been substantially smaller than amongst the UK white population, suggesting that current approaches to risk stratification and intervention are less effective and require further optimisation for the South Asian ethnic group.⁸

Risk factors for T2D and CVD in South Asian populations

To date, few studies have assessed the incidence of T2D and CVD, or the relationship of these diseases to baseline risk factors in South Asian populations. Further, the available, completed investigations have all limited by small sample size and focus on a narrow range of geographic settings (typically single city). 9,10 Although the WHO and others have proposed tools for prediction of CVD amongst South Asian populations, these tools have major limitations. In particular, risk prediction tools such as GLOBORISK are derived based on: i. risk relationships observed in exclusively European and North American populations, ii. the prevalence of CVD risk factors amongst South Asian derived from small-scale population surveys, and iii. WHO estimates for country specific CVD mortality rates derived from verbal autopsy studies (the Sample Registration System, comprising ~6M across ~1M households).11 The validity of these assumptions is uncertain, and may explain the paradoxical observation that GLOBORISK predicts young South Asians to be at higher risk of CVD compared to elderly South Asians, for the same risk factor burden. As a result of these limitations, there is a deficiency of knowledge to inform approaches for accurate quantification of risk for T2D and CVD amongst South Asians, that can be used to inform national or state healthcare policy amongst the ~1.7 billion South Asians on the Indian subcontinent.

Existing frameworks for monitoring CVD and T2D in South Asia

Accurate knowledge concerning the burden and future trajectories of CVD and T2D, is also central to the delivery of effective healthcare interventions and of health policy for prevention and control of these non-communicable diseases (NCDs). The information delivered by NCD surveillance enables prioritisation of resource allocation, as well as evaluation of healthcare and health system interventions for impact, including clinical impact and cost-effectiveness.

Current systems for surveillance of NCDs such as CVD and T2D in South Asia, are fragmented and incomplete. For example, in Pakistan the WHO STEPS survey of NCDs carried out in 2014 included just 7,700 people from 2 states, relied on self-reported disease, did not collect biological sample for diagnosis of T2D, and made no assessment of quality of care for T2D or CVD. Similar limitations apply to current surveillance data for Bangladesh and Sri Lanka. In India, the INDIAB study of T2D burden and control amongst ~57,000 people from 15 states represents a step change for surveillance of T2D in the region, and provides valuable insights into the heterogeneity in disease risk that exist even within one country. However, the cross-sectional design of INDIAB, and the lack of data for CVD, limit utilization of these data for the wider impact for NCD healthcare and health system interventions. The absence of nationally representative data concerning the burden of NCDs, and behavioral and clinical risk factors in South Asia, is a major challenge in the fight against NCDs in the region, and contributes to widen global health inequality in South Asia.

There is a major need for improved understanding of the burden of T2D and CVD across South Asia, and of the underlying determinants of these major diseases, to underpin both targeted and population-based approaches for disease prevention, in South Asians.

1.2 RATIONALE FOR CURRENT STUDY

The burden of T2D and CVD is especially high in South Asia. T2D affects ~56 million people, and CVD ~62 million people in India alone. The number of people affected by T2D and CVD in South Asia will double by 2030; contrasting stable or falling rates in Europe and the US. T2D and CVD pose an enormous economic burden on individuals, families and healthcare systems of South Asia, and contribute to increasing poverty, widening health and social inequalities and regional instability. The lack of evidence to inform healthcare policy for T2D and CVD in these environments, contributes to the continued rise of these diseases in South Asia, and to widening global inequality. T2D and CVD are identified as the leading public health challenges in all South Asian countries.

Benefits to society. Through our research, we will provide robust data on the burden and quality of care in South Asia. The information collected will inform priorities for healthcare providers and policy makers, and facilitate transformation of health systems in South Asia. Effective actions based on our findings (eg through guidelines, quality standards and high-quality training) will help improve efficiency, effectiveness and quality of healthcare in South Asia. Our actions are thus directly designed to promote the health needs and welfare of the people living in South Asian countries, and thereby reduce global health inequalities, regional instability and poverty.

Benefits to individuals. As part of our surveillance exercise, we will provide structured individual reports to participants that detail the results of their health assessment, and provide clear written advice for suitable measures to improve health and well-being. Furthermore, participants will be reviewed by the study Medical Officers to provide specific interpretation, explanation and guidance concerning the personal health report, and the surveillance team will facilitate onward referral of participants identified with health risks for further appropriate treatment. We this bring direct benefit to individual participants.

Sustainability and future directions

The UK National Institute for Health Research (NIHR) has provided funding to establish and maintain the network of surveillance sites for the first three years. The lead organization in each country/region has committed to maintaining the NCD surveillance program beyond the four-year interval. The Chief Investigator, Steering Committee and other scientists and clinicians involved in the study, are additionally committed to obtaining ongoing funding beyond the initial award from NIHR, to enable the late outcomes of the research (>20 years) to be determined.

2. STUDY OBJECTIVES

This project represents a collaboration between academic and clinical experts in NCD prevention and control from leading institutions in Bangladesh, India, Pakistan, Sri Lanka and the UK. With initial 4-year funding from the UK National Institutes for Health Research, we will pursue a program of translational research in South Asian that aims to:

- Strengthen NCD surveillance systems in Bangladesh, India, Pakistan and Sri Lanka, by establishing a network of >200 surveillance sites across these South Asian countries.
- Using standardised approaches, complete structured assessments on a representative sample of ~160,000 South Asian men and women aged 18+ years, living at the >200 surveillance sites. Collect and store biological samples for epidemiological purposes.
- In the longer-term, continue longitudinal follow-up of the 160,000 people screened, to ascertain fatal and non-fatal NCD outcomes. Thereby enable quantification of NCD risk relationships, including identification and evaluation of disease biomarkers.
- In addition, use a subset of the surveillance sites as Health observatories for evaluation of healthcare interventions targeted at improving prevention and control of T2D and CVD in South Asia.
- Thereby provide the first robust, nationally representative data on the burden of T2D, CVD and their risk factors, and on the quality of care for these major NCDs to quantify needs, in South Asian populations.
- Disseminate the data to relevant stakeholders, include health service providers and policy makers to inform resource allocation and health system priorities. In addition, use the clinical data and biological samples collected, to pursue epidemiological research into aetiological mechanisms underlying the increased risk of T2D and CVD in South Asians.

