We will study at least 40 surveillance sites in each of the 5 study regions (Bangladesh, India North, India South, Pakistan, Sri Lanka; N>200 sites in total). Selection of sites will be done in such a way that we are able to generate credible estimates on burden of CVD and T2D, and their risk factors from a sample that are representative of the country, rural and urban areas separately and for each of the major administrative regions. In outline, site selection for each country/region will be as follows:

Bangladesh. We will select 42 sites, distributed across the entire country (**Appendix 2**). Bangladesh has 8 divisions, with substantial variation in population size between divisions. In addition, the Chittagong Hill Tracts (CHT), which comprise 3 districts, are different from the rest of Bangladesh with respect to population density and ethnicity. We will select 40 surveillance sites from the 8 divisions (excluding the CHT), with the number of surveillance sites in each division being proportionate to the population size of the division. In addition, we will chose a further 2 surveillance sites from CHT (thus N=42 total). The number of rural and urban sites within a division will be proportional to the rural and urban population with a condition that there will be at least 1 urban site in each of the division. The CHT will have 2 rural sites.

The surveillance sites will be selected using a multistage sampling approach. For the selection of rural sites we will randomly select one district from each division and the CHT. We will then randomly select one sub-district from the district/CHT. Afterwards, one or more community clinics (CC) will be selected from the respective sub-district depending on the number of rural sites within the district. The ward in which the CC is located will be our rural surveillance site. For the selection of urban sites, one urban dispensary (UD)/CC will be randomly selected from each of the 12 city corporations. The *mahalla* in which the UD/CC is located will be the urban surveillance site. If the ward/mahalla is too large and has more than 2000 population, we will divide the ward/mahalla into segments. The segment that has the CC/UD will be our surveillance site. Everyone who meets the inclusion criteria within the selected site will be recruited in the surveillance.

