India North. We will focus on 40 surveillance sites located in the South Delhi Municipal Corporation (SDMC), in the Delhi National Capital Region (NCR). SDMC serves a population of ~10M people, with diverse demographics characteristics, and includes both urban and rural villages. The South and Najafgrah zones of SDMC will be classified as one hub, while the Central and West zone will be classified as the second hub. We will compile a list of the basic health care units in each SDMC zone (Appendix 2), and classify each as urban / rural based on governmental data. If a health care unit caters to a large population (>50,000), the area will be divided into smaller colonies of 10-50,000 people. From this compiled list of SDMC locations, we will then select 40 surveillance sites at random, but including urban and rural locations in a 1:1 ratio. The population catered to by the health care units will be mobilised by the ASHA workers affiliated to the established surveillance sites.

India South. We will conduct surveillance in both urban and rural areas. The surveillance sites will be villages in rural areas and census enumeration blocks (CEBs) in urban areas. The ultimate stage units will be households in both areas. The rural component of the surveillance is planned to be conducted in 25 selected villages in Cheyur taluk (Appendix 2), which is situated in Kancheepuram district of Tamil Nadu state in southern India. All individuals who meet the inclusion criteria in each household within the selected villages will be invited to participant in the surveillance (n=20,000).

The urban component of the surveillance will be carried out in Chennai, which has a population of 10,705,000 individuals. Chennai is divided into 15 zones and 200 wards by the Chennai Corporation. Of the 200 wards, 40 wards will be randomly selected to represent all 15 zones of the Corporation of Chennai. From the selected 40 wards, 10 Census Enumeration Blocks (CEBs) will be randomly selected from each ward (n=400). The next stage of sampling will be based on systematic sampling where 50 households from each CEB will be selected

with a random start. One individual will be selected using the WHO KISH method and meets the inclusion criteria in each household will be invited to participant in the surveillance (n=20,000) (Appendix 2).

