Pakistan. Pakistan has a population of ~214M people, and is divided administratively into four provinces (Balochistan, Punjab, Sindh, Khyber Paktunkhwa) and the Islamabad Capital Territory (ICT). Each province is further divided into divisions, towns and union councils. The union council is the smallest division, and typically consists of ~30,000 people. Each union council has basic health unit and outreach staff. The union council will be our sampling unit for surveillance.

We will focus the surveillance project on the Punjab Province, the most populated state of the country (N=110M). We will aim to establish surveillance sites in each of the 36 states that comprise the Punjab Province, distributed between in proportion to population size, with approximately 1 site per 3 million population. Surveillance sites will be selected using a multistage sampling approach. During the first stage, target towns will be selected for each province, based on population size of the province (one town per 5-6 sites). In each town, the available administrative lists of union councils will be used to select rural and urban union councils in a 1:1 ratio. As stage 1, surveillance will start in central Punjab (Appendix 2), and will be extended to North and South Punjab on successful completion of stage 1.

Sri Lanka. Sri Lanka has 9 Provinces, that are in turn divided administratively into 25 Districts, and then into further administrative units of which the smallest is the Grama Niladhari (GN). We will select 100 surveillance sites from all the districts and provinces. Each site will have 500 persons eligible to be a participant of the surveillance. The number of surveillance sites for each province will be proportionate to the population size of the province. The number of sites for each district within a province will again be proportionate to the population size of the district. Within a district we will allocate the surveillance sites based on the proportion of rural and urban population. The provisional allocation of surveillance sites by district and province is summarized in Appendix 2.

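### The national-representativeness claim is not supported by the India and Pakistan sampling frames, which supply 100,000 of the 160,000 target participants

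*Protocol*

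**What the plan says.** **The claim.** Among the aims in Section 2 is: "Thereby provide the first robust, nationally representative data on the burden of T2D, CVD and their risk factors". The same objective covers quality of care. Section 3, under selection of surveillance sites, applies the idea to all five regions: credible estimates are to come "from a sample that are representative of the country, rural and urban areas separately and for each of the major administrative regions".

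**The frames for India and Pakistan (Section 3).**
- India North: "We will focus on 40 surveillance sites located in the South Delhi Municipal Corporation (SDMC), in the Delhi National Capital Region (NCR". This corporation serves about 10M people.
- India South, rural: "25 selected villages in Cheyur taluk", in one district of Tamil Nadu (n=20,000).
- India South, urban: "The urban component of the surveillance will be carried out in Chennai, which has a population of 10,705,000 individuals" (n=20,000).
- Pakistan: "We will focus the surveillance project on the Punjab Province, the most populated state of the country (N=110M". Work begins in central Punjab and moves to the north and south of the province only after that stage succeeds.

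Appendix 2 agrees: Table 2.2 lists only Delhi areas and Table 2.4 only Punjab districts.

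**The frames for Bangladesh and Sri Lanka (Section 3).** Sites are spread over all eight divisions plus the Chittagong Hill Tracts in Bangladesh, and over all provinces and districts in Sri Lanka.

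**Weighting (Section 7).** Sample weights for the multistage design will be used in the descriptive analysis.

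**The concern.** A prevalence is nationally representative in the design-based sense only if every part of the country had some chance of selection. In India and Pakistan most places had none. Sections 2 and 3 thus assert a property that the sampling plan does not have, and no other part of the protocol qualifies the assertion.

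This affects use. Section 2 wants the burden data to inform resource allocation, and Section 9 sets up country committees so that the findings enter national policy making and reporting to global bodies. A Delhi, Chennai or Punjab figure taken as national could misdirect either.

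The protocol's own background (Section 1.1) criticises earlier work for narrow geography, often one city, and a 2014 survey in Pakistan for covering two states. It also credits a 15-state Indian survey with showing how much risk varies inside one country.

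**Working it through.** **1. Reproduce the total.** Table 1 targets: Bangladesh 30,000 + North India 30,000 + South India 40,000 + Pakistan 30,000 + Sri Lanka 30,000 = 160,000. This matches the stated total.

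**2. Share from sub-national frames.** North India 30,000 + South India 40,000 + Pakistan 30,000 = 100,000. 100,000 / 160,000 = 62.5%. Bangladesh and Sri Lanka give the other 60,000 (37.5%).

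**3. Coverage in Pakistan.** Section 3 gives 110M for Punjab and about 214M for the country. 110 / 214 = 51.4%, so 48.6% of the population lies outside the frame even if every stage is completed. The share is lower if the work stops after central Punjab; the documents give no population for that part.

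**4. Coverage in India.** The frames named are about 10M (the Delhi corporation) and 10.705M (Chennai), plus one taluk of unstated size. The protocol gives no population for India, so I compute no share.

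**5. Why weights do not help.** A design weight is the inverse of the selection probability. It corrects unequal probabilities inside a frame. Where the probability is zero the weight is undefined, and the area contributes nothing to the estimate.

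**6. What the printed precision covers.** Table 4 is reproduced by the 95% half-width 1.96 × √(p(1−p)/n), under simple random sampling:

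| Prevalence | n=160,000 | n=30,000 | n=750 |
|---|---|---|---|
| 30%, computed | 0.22 | 0.52 | 3.28 |
| 30%, Table 4 | 0.2 | 0.5 | 3.3 |
| 20%, computed | 0.20 | 0.45 | 2.86 |
| 20%, Table 4 | 0.2 | 0.5 | 2.9 |

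(percentage points). The printed figures therefore describe sampling error only and contain no term for coverage.

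**7. Illustration of scale (assumed inputs).** National prevalence = 0.514 × Punjab + 0.486 × rest. The error from reading Punjab as Pakistan is then 0.486 × (Punjab − rest). The documents do not give that difference. For assumed differences of 1, 2 and 5 points the error is about 0.5, 1.0 and 2.4 points. This takes the total-population share as the adult share. Recruiting more people inside Punjab would not reduce it. The finding does not depend on this illustration.

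**8. The other two frames.** Their geographic spread is national, but the same zero-probability test finds gaps:
- Sri Lanka (Section 3): only Grama Niladhari divisions with a specified type of health facility are listed. In a division above 1,000 people, only the segment holding the facility is used.
- Bangladesh (Section 3, Table 2.1): sites are built around a community clinic or urban dispensary. In a ward or mahalla above 2,000 people, only the segment holding it is used. Urban sites come only from city corporations.

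**The case against.** The best reply is that the frames are openly named in Section 3 and Appendix 2, so nobody is misled, and that much of the study does not need a national sample. The second half stands in full: the risk-association, biomarker and aetiology aims do not rest on national representativeness. The first half does not remove the conflict. Naming a frame does not narrow a claim that Sections 2 and 3 leave unqualified, and burden and quality of care are separate objectives that do need coverage. A statistical analysis plan could not cure this either, since it cannot extend a frame.

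Four stronger readings are tempting, and the documents do not support them:
- A reader might infer that Bangladesh and Sri Lanka are, by contrast, nationally representative. Step 8 shows areas in both that could not be selected. Wide spread is established; full representativeness is not.
- A reader might take the Country column of Table 4 as a claim of national precision for India or Pakistan. The protocol uses country and region interchangeably, and 30,000 is the target of four of the five regions. It is loose labelling.
- A reader might conclude that the frames show no heterogeneity at all. India has two separate regions, each with urban and rural parts, and Section 7 plans to explore regional differences. Coverage is limited, not nil.
- A reader might say that the estimates will be published as country prevalences. No section says so of a particular regional estimate. The risk comes from the unqualified objective together with the intended policy use.

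**Conclusion.** The point holds, limited to the burden and quality-of-care claim. Sections 2 and 3 state national and administrative-region representativeness; the frames for India and Pakistan cannot deliver it; 62.5% of the target sample comes from those frames. In Pakistan at most 51% of the population is within reach, by the protocol's own figures. This assumes that the Table 1 targets are met and that the frames in Section 3 and Appendix 2 are the ones used. It is an overclaim that conflicts with the sampling section. It does not show that the choice of frames was wrong, which may have been deliberate. It should be corrected, because it changes what the study may conclude.

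**What to change.** In Section 2 and in the site-selection paragraph of Section 3, replace the national claim with the population sampled in each region:
- India North: the South Delhi Municipal Corporation.
- India South: Chennai and the selected Cheyur villages.
- Pakistan: the part of Punjab actually sampled.
- Bangladesh and Sri Lanka: frames spread across all divisions or provinces, but limited to areas or segments containing a listed health facility, with Bangladesh urban sites from city corporations only. Do not assert full national representativeness.

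Add a sentence that no India, Pakistan or pooled South Asia prevalence or quality-of-care estimate will be reported as national. As a minor consistency edit, relabel the Country column of Table 4 as Country/region.

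No site, sample size or procedure changes. The cost is a more modest burden objective and a narrower site-selection criterion.
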